Over 150,000 ventral and incisional hernia repairs are performed annually in the United States ². Reinforcing the fascial closure with mesh has dramatically reduced recurrence rates by as much as 50-70%. Synthetic mesh has been shown to provide durable long-term outcomes; however, its use is contraindicated in contaminated fields. Contaminated and dirty wounds include a spectrum of operations involving opening or anastomosis of the GI tract, reoperation at the sites of on-going or previous infection, fistula, or abscess, infected foreign body, and major break in sterile technique. If a permanent synthetic mesh is used under such circumstances, there is greater than 50% risk of developing subsequent infection or persistent draining sinus as the synthetic mesh can harbor bacteria and prevent the host immune system from eradicating the infection even with adequate antibiotic treatment ³. In the majority of these cases (50-90%), the mesh has to be surgically excised to enable the wound to heal ⁴.

To address the challenge of prosthetic reinforcement in contaminated fields, biologic grafts or meshes have been developed. Biologic mesh is made of an acellular collagen matrix derived from dermal, fascial, pericardial, or other tissues. Strattice® (LifeCell Corporation, Branchburg, NJ, USA) is a common biologic mesh originating from porcine dermal matrix. Biologic meshes allow the body to eradicate small amounts of bacterial contamination (up to 10⁴ CFU/ml) by promoting tissue in-growth into the mesh collagen matrix. Porcine derived biologic meshes have been shown to clear bacterial infection with *Staphylococcus aureus*. Strattice was demonstrated to be most effective among porcine meshes at lowering bacterial counts⁵ and has been shown to provide equivalent integrity and strength of hernia repair in animal models⁶. However, in the same animal models followed over longer periods of time, we have seen both animal and human derived biologic meshes lose their integrity and tensile strength when exposed to bacterial loads at the time of implantation⁷. The impact of this phenomenon has been documented in humans, but its clinical relevance and impact on long term results has not been tracked.

In recent years, bioabsorbable, non-tissue derived products have been developed as an alternative to biologic mesh. Bioabsorbable mesh employs the same principals as biologic mesh by promoting tissue

[figure not shown]
[figure not shown]
[figure not shown]
in-growth and neovascularization but was developed to address the weaknesses of biologics. Bio-A® (W. L. Gore & Associates, Inc., Newark, DE, USA) is a bioabsorbable mesh composed of 67% polyglycolic acid and 33% trimethylene carbonate commonly used in the reinforcement of soft tissue. Identical chemical composition is used in making some sutures and Seamguard®, a product used in the reinforcement of staple lines. These are inert materials, neither of which has been known to stimulate allergic reactions in human subjects. Bio-A is constructed as a non-woven web that acts as a scaffold for tissue in-growth and is absorbed in the body within approximately 6 months.⁸ Furthermore, the use Bio-A offers healthcare providers and patients significant cost savings over biologics, as much as 66% per square centimeter.⁹

Although our own animal studies (see below) have demonstrated improved tissue in-growth and collagen deposition with bioabsorbable mesh compared to biologic porcine-derived material, no randomized, prospective, blinded study comparing these two mesh types is available nor has there been long term follow-up which includes quality of life measures in humans. Therefore, we propose a randomized, prospective, blinded clinical trial of patients with grade II or III ventral hernias according to Ventral Hernia Working Group (VHWG) classification that will compare outcomes of Strattice versus Bio-A. Grade II hernias are those in patients with certain comorbidities (diabetes mellitus, immunosuppression, current tobacco use, COPD, or BMI>30) that have been associated with higher rates of wound infections. Grade III hernias are considered to be potentially contaminated due to previous wound infection, presence of intestinal stoma, or violation of gastrointestinal tract¹. Grade IV hernias are those in contaminated fields (current mesh infection, septic dehiscence), and these hernias will be excluded from this study.

An appropriate prospective, randomized, double-blind clinical trial comparing the outcomes of Strattice and Bio-A in patients who would benefit from them most is absolutely needed and will allow surgeons to contrast results in an effort to decide which material will improve the outcomes of their patients with complicated abdominal wall defects.

Preliminary Data

We have previously evaluated tissue in-growth, collagen deposition and vessel formation of Bio-A and Strattice in sterile fields in a rabbit model. Grafts were implanted subcutaneously and harvested at 7, 14, 60, 90 and 180 days. The results are shown below.

Bio-A exhibited a higher degree of cellular in-growth, neovascularization, and collagen deposition than Strattice; however, we would like to evaluate use of both of these mesh types in at-risk patients to determine if one mesh produces superior outcomes in comparison to the other.

Materials and Methods - Patient Enrollment:

This is a prospective, randomized study. Study subjects will include patients classified as grade II and grade III according to VHWG classification scheduled for elective or non-emergent open ventral hernia repair.

Patients will qualify for this study if they meet the following criteria:

- Age 18 or older
- Grade II or III ventral hernia according to VHWG classification system
- Pre-operative informed consent is obtainable

Patients will be excluded from the study if they meet the following criteria:

- Return to the operating room within the next 1 year for additional open abdominal surgery is anticipated
- Absence of fascial defect or fascial defect less than 3 cm in greatest dimension
- Presence of previously placed mesh (synthetic or biologic) at the site of surgery, which will not be completely removed and will, in part or in whole, remain at the site of implantation of the study mesh
- Concurrent placement of another mesh (synthetic or biologic) at the site where the study mesh is placed
- Grade IV ventral hernia according to VHWG system
- ASA¹ score IV or above
- Any disease or condition along with the surgeon's clinical judgment that contraindicates the use of either study mesh
- Pregnancy
- Use of more than one of the same study mesh is not an exclusion criterion in and of itself, so long as the type of mesh is selected according to the randomization protocol

During pre-operative evaluation, patients will be informed about the details of the proposed study including the use of mesh, methods and possible risks of the procedure as well as possible side effects associated with the use of mesh. Implantation of either mesh product should not increase the risk of post-operative morbidity. The patients will be informed that the use of non-permanent mesh is clinically indicated in their condition and the determination to use a non-permanent mesh intra-operatively will be made entirely on clinical grounds and not based on the research protocol. If a non-permanent mesh is required (biologic or bioabsorbable), the randomization of the study will prescribe which type of mesh will be used. To date, there is no evidence to suggest that either one of the study meshes is superior or safer than the other. Patients willing to enroll must be able to give their informed consent to a research coordinator, which will include permission to collect data, distribute surveys and contact them after surgery for educational and research purposes.

Patient Randomization:

Randomization will be performed by a certified statistician using a computerized algorithm. Stratified randomization will be used based on the demographics, comorbidities and nature of any potential

¹ American Society of Anesthesiologists

contamination in order to maximize the likelihood of balanced groups. Patients will remain unaware of their group assignment or implanted mesh type throughout the duration of the trial.

Peri-Operative Care:

On the day of surgery, each patient will be randomized into one of two mesh groups. A group assignment letter in a sealed opaque envelope will be placed into patient's chart. The chart will be marked with a sticker indentifying the patient as part of proposed clinical study. Prior to taking the patient back to the operating room, the circulating nurse will check that the patient is appropriately consented and understands he/she is enrolled in the study. Furthermore, the circulating nurse is responsible for ensuring that the sealed envelope is in the chart and has not been opened. Following patient transfer to the operating room and induction of anesthesia, the circulating nurse will perform a "time-out", where he/she reads the consent form and notifies the operating room that the patient is part of the proposed study. As part of the time-out, the circulating nurse will open the sealed envelope and announce the mesh assignment to the surgical team prior to incision. This will give sufficient time for the staff to locate all necessary materials.

Materials:

The study meshes:

- Strattice® (LifeCell Corporation, Branchburg, NJ, USA)
- Gore®Bio-A® (W. L. Gore & Associates, Inc., Newark, DE, USA)

as well as adjunct fixation materials will be drawn from the Operating Room supply. A member of the research team will ensure adequate stock of both mesh types. The size of the mesh will be determined by the operating surgeon. Unless otherwise clinically indicated, surgeons will obtain at least a 5 cm mesh-fascial overlap for the hernia repair, except possibly at the pubis or xiphoid process. The mesh is to be secured to the fascia using Prolene™ Polypropylene Suture (Ethicon, Inc., Hamburg, Germany) size 0 or greater on a non-cutting needle. Alternatively, an equivalent size polypropylene monofilament suture may be used. If more than one piece of subject mesh is required, the pieces must be sewn together with a running 0 polypropylene suture with interrupted stitches of 0 polypropylene every 1.5cm. The mesh pieces may be of different sizes, however, all pieces must be of the same material as per the group assignment. Use of more than one type of mesh will result in disqualification from the study.

Procedure for Repair of Abdominal Defect:

In both groups, patients will receive underlay mesh tissue reinforcement followed by standard fascial closure with #1 PDS. This technique will require the surgeon to develop a plane between the rectus muscle and the posterior rectus sheath or the peritoneum and fascia for mesh placement. The mesh product will be placed in the developed space under the defect. As mentioned above, in a rare case when larger piece of mesh is required, a second packet of mesh will be opened and the mesh will be sutured together as previously mentioned. As described by [name]⁻¹², the mesh will be secured via non-absorbable, full thickness, abdominal wall sutures. Two interrupted sutures will be used to anchor the mesh superiorly and two interrupted sutures will be used inferiorly. Additional full thickness sutures will be placed every 8 cm circumferentially. After securing the mesh in place, #1 PDS sutures will be used to close the fascia in a running fashion with 1.5-2 cm "bites" from the fascial edge and a 1cm "walk" between stitches. Skin will be closed with staples or monofilament suture

according to surgeon preference. One or two drains will be placed on the mesh in each case, and one or two drains will be placed in the subcutaneous tissues at the discretion of the surgeon depending on the amount of subcutaneous tissue dissected.

To qualify for the study, the fascia must be closed completely and without tension. A posterior rectus release to relax the fascial closure will be allowed, but a formal components separation, with laceration of the external oblique, will disqualify a patient from the study. A mesh bridge is not allowed and will result in disqualification from the study. Aside from this restriction, mesh may be placed in the preperitoneal or retrorectus position. Careful documentation by the operating surgeon of all of the repair components is imperative to avoid introducing bias, as well as precise description of the number of transfascial fixation sutures and additional fixation modalities.

Post-Operative In-Hospital Care:

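### Patients are disqualified from the study for operative events after unblinded randomisation, which, read literally, removes them from the ITT analysis that decides efficacy

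*Combined protocol and SAP*

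**What the plan says.** The order of events is clear. Under Peri-Operative Care, "On the day of surgery, each patient will be randomized into one of two mesh groups". After induction of anaesthesia, "the circulating nurse will open the sealed envelope and announce the mesh assignment to the surgical team prior to incision".

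Four operative rules then apply:

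- Materials: "Use of more than one type of mesh will result in disqualification from the study".
- Procedure for Repair of Abdominal Defect: "To qualify for the study, the fascia must be closed completely and without tension".
- Same section: "a formal components separation, with laceration of the external oblique, will disqualify a patient from the study".
- Same section: "A mesh bridge is not allowed and will result in disqualification from the study".

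The Procedure section adds that "Careful documentation by the operating surgeon of all of the repair components is imperative to avoid introducing bias".

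Data Analysis and Statistics plans both an ITT and a per-protocol analysis and lets ITT determine efficacy if the two differ significantly. It defines neither set. No section says whether a disqualified patient is followed, or stays in the ITT set.

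**The concern.** Every one of these events is settled after randomisation, by people who know the assigned mesh. The early announcement is not itself an error. The problem is that the stated consequence is removal from the study, not from one analysis set.

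Components separation, bridging and tense closure are plausibly related to defect size and to recurrence risk, and recurrence is a primary outcome. If such patients leave the analysis, the decisive comparison is no longer between all randomised patients. On the literal reading, both analysis sets lose the same patients, so comparing ITT with per-protocol would not expose the problem. If sites also stop follow-up, the missing outcomes cannot be recovered later.

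**Working it through.** **Reading the sections together**

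| Point | Literal reading (out of the study) | Milder reading (out of per-protocol only) |
|---|---|---|
| Materials and Procedure sections | Wording refers to the study, not to an analysis set | Needs words that are not there |
| Patient Enrollment | Uses the same verb for eligibility ("Patients will qualify for this study if they meet the following criteria") and lists concurrent placement of another mesh, which overlaps the mixed-mesh rule, as an exclusion from the study | The list can be read as pre-operative only |
| In-hospital care and follow-up | Silent on whether a disqualified person is still a study patient | Refer to patients without limit |
| Data Analysis and Statistics | ITT is decisive but would lack randomised patients | Consistent |

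The Patient Enrollment wording favours the literal reading without settling it. The documentation duty secures operative data but is not an analysis rule.

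**Illustration of size**

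The protocol gives no disqualification or recurrence rate, so there is no figure of the plan to reproduce here. Inputs from the protocol: 48 recruited per arm, 20% attrition, effect size 0.85, significance level 0.05 (taken as two-sided), chi-square and Fisher tests. Assumptions: true recurrence 20% in both arms, risk r in removed patients of 40% or 60%, share removed q of 5-20%.

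Recurrence among the patients who remain = (0.20 - q·r)/(1 - q):

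- q = 0.05: 0.1895 (r = 0.40), 0.1789 (r = 0.60)
- q = 0.10: 0.1778, 0.1556
- q = 0.20: 0.150, 0.100

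The false difference is the gap between the arms. For 10% removal from one arm and none from the other it is 0.20 - 0.1778 = 0.022 to 0.20 - 0.1556 = 0.044. For 10% against 20% it is 0.1778 - 0.150 = 0.028 to 0.1556 - 0.100 = 0.056.

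False-positive rates by exact enumeration, as ranges over r = 0.40 to 0.60 (equal removal: over both r and q):

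| Removal | n per arm | False difference (points) | Chi-square | Fisher |
|---|---|---|---|---|
| None | 48 v 48 | 0 | 5.2% | 2.7% |
| 0 v 5% | 48 v 46 | 1.1-2.1 | 5.4-5.9% | 3.6-4.0% |
| 0 v 10% | 48 v 43 | 2.2-4.4 | 6.0-8.6% | 4.3-6.4% |
| 10% v 20% | 43 v 38 | 2.8-5.6 | 6.4-11.2% | 4.2-7.5% |
| Equal, 10% or 20% | 43 v 43 or 38 v 38 | 0 | 5.3-5.8% | 1.5-2.5% |

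With 20% attrition added:

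| Removal | n per arm | Chi-square | Fisher |
|---|---|---|---|
| None | 38 v 38 | 5.0% | 2.7% |
| 0 v 5% | 38 v 36 | 5.1-5.4% | 3.7-4.0% |
| 0 v 10% | 38 v 35 | 5.8-8.0% | 4.3-6.1% |
| 10% v 20% | 35 v 31 | 5.7-9.1% | 4.3-6.5% |

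A difference of 2.2 points on 43 patients is 0.022 × 43 = 0.95, about one event.

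**Power**

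With 20% disqualified on top of 20% attrition, 48 × 0.8 × 0.8 = 30.7, about 31 per arm. A two-sample t-test at effect size 0.85 then has power of about 0.91. Loss of power is not the concern.

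**The case against.** The best counter-argument is that the statistics section makes most sense on the milder reading. A per-protocol set needs protocol departures, and these operative rules are the most explicit departures in the document. If the patients concerned left both sets, the two analyses would largely coincide and the rule giving ITT the last word would have little to do. The Patient Enrollment list also sits under enrolment, and some of its items are anticipatory.

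This shows that the milder reading is plausible, perhaps intended. It does not put it in the text, and site staff will act on the text.

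It is also fair that the size rests wholly on assumed rates, that only recurrence was modelled, and that one technique is prescribed for both groups, so nothing shows that removal would differ by arm. Fisher exceeds 5% only with 60% risk in removed patients and a 10-point gap in removal. All of that stands, and it limits the claim to possible bias.

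One further point stands. Patient Enrollment leaves the decision to use a non-permanent mesh to the operation itself, so it too can fall after randomisation. An ITT set of all randomised patients covers those cases, but the per-protocol set needs a rule for them. The protocol is also silent on whether disqualified patients are replaced.

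**Conclusion.** The concern holds: as written, the operative rules take randomised patients out of the study and conflict with an ITT analysis that decides efficacy. This must be fixed before the analysis sets can be relied on. The conclusion rests on the wording and the order of events, not on the illustrative numbers.

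Under the assumed rates the distortion runs from negligible (5% excess removal) to a chi-square false-positive rate of 11.2% (10% against 20%, risk 60%, no attrition). It is nil for equal removal at equal risk. If all randomised patients are in fact kept and followed, ITT is protected and only the per-protocol set is affected.

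**What to change.** Reconcile Patient Enrollment, Materials, the Procedure section and Data Analysis and Statistics by stating that:

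1. The ITT set is all randomised patients, analysed in the assigned arm.
2. All of them are followed on the existing schedule to 36 months.
3. Disqualification, and failure of the closure condition, remove a patient from the per-protocol set only. The same holds when the concurrent-mesh exclusion arises during the operation.
4. Disqualifications and their reasons are reported by arm, from the operative documentation already required.

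The same edit should give the per-protocol status of patients in whom no non-permanent mesh is used, and say whether disqualified patients are replaced. The surgical rules and the timing of envelope opening stay as they are.

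**Cost.** Wording, plus follow-up of disqualified patients. At an assumed 10-20% rate that is 10-19 of 96 patients, and over five visits at most 10 × 5 = 50 to 19 × 5 = 95 visits.

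Keeping these patients may dilute the ITT contrast. In the worst case, where they carry no mesh contrast at all and the SD is unchanged, the effect size falls to 0.85 × 0.90 = 0.765 or 0.85 × 0.80 = 0.68. Power at 38 per arm (48 × 0.8 = 38.4) then falls from 0.955 to 0.908 or 0.833. The real loss should be smaller, because a patient with a components separation or a bridge can still carry the assigned mesh.

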Patients will undergo post-operative follow-up at 1 month, 6 months, and yearly for 3 years. Patients will receive reminders of their follow-up visits before each time period. If the patient is not receiving follow-up assessment from [name] and his associates, we will also send a provider letter for the provider as well as a physician assessment that will be completed by the new provider. At each visit, patients will be asked to fill out a short questionnaire (Form A and Form B, attached) that will aid in assessing and documenting postoperative symptoms and quality of life. During each follow-up visit a board certified or board eligible surgeon, who is blinded with regard to the group assignment, will perform a physical examination to assess for the presence of a recurrent hernia, eventration and other findings detailed on Form C (attached). Any signs of wound complications will be noted, including seroma formation, erythema, drainage, break in the skin, purulence or tenderness to palpation. If a recurrent hernia defect is identified on the physical examination, imaging studies will be performed as indicated. Once a hernia defect is found, further management options will be discussed with the patient. Routine imaging will not be performed as the physical examination has been the gold standard for diagnosing abdominal hernias in previous large randomized multicenter studies¹³⁻¹⁴.

Data Analysis and Statistics

Demographics, comorbidities, preoperative conditions and the nature of contamination will be recorded as well as post-operative hospital course and follow-up findings, including drain outputs, the use of antibiotics and drainage procedures, and postoperative quality of life surveys. The latter along with hernia recurrences and specific wound complications will be used as primary outcome variables.

A power analysis yielded a sample size of 96 patients. With an expected effect size of at least 0.85, it was determined that 40 patients in each group will be needed to show significance at the 0.05 level with 90% statistical power. In order to accommodate for a 20% attrition rate, 48 patients will be recruited into each group. Statistical analysis will be performed using SAS® System version 9.3 (SAS, Cary, NC, USA). Both intent-to-treat (ITT) and per protocol analysis will be performed. If the results of these two analyses significant differ, efficacy will be determined by the ITT analysis.

13. Stoppa RE. The treatment of complicated groin and incisional hernias. *World J Surg*. Sep-Oct 1989;13(5):545-554.

Carolinas Comfort Scale™

Carolinas Medical Center

*Division of Gastrointestinal and
 Minimally Invasive Surgery*

Name: _____

Date of Surgery: _____

Date of Survey: _____

0 = No symptoms
 1 = Mild but not bothersome symptoms
 2 = Mild and bothersome symptoms
 3 = Moderate and/or daily symptoms
 4 = Severe symptoms
 5 = Disabling symptoms

Please answer ALL questions for each of the 8 activities.

Use N/A if an activity was not performed.

1. While laying down, do you have							
a) sensation of mesh	0	1	2	3	4	5	N/A
b) pain	0	1	2	3	4	5	N/A
2. While bending over, do you have							
a) sensation of mesh	0	1	2	3	4	5	N/A
b) pain	0	1	2	3	4	5	N/A
c) movement limitations	0	1	2	3	4	5	N/A
3. While sitting up, do you have							
a) sensation of mesh	0	1	2	3	4	5	N/A
b) pain	0	1	2	3	4	5	N/A
c) movement limitations	0	1	2	3	4	5	N/A
4. While performing activities of daily living (i.e. getting out of bed, bathing, getting dressed), do you have							
a) sensation of mesh	0	1	2	3	4	5	N/A
b) pain	0	1	2	3	4	5	N/A
c) movement limitations	0	1	2	3	4	5	N/A
5. When coughing or deep breathing, do you have							
a) sensation of mesh	0	1	2	3	4	5	N/A
b) pain	0	1	2	3	4	5	N/A
c) movement limitations	0	1	2	3	4	5	N/A
6. While walking, do you have							
a) sensation of mesh	0	1	2	3	4	5	N/A
b) pain	0	1	2	3	4	5	N/A
c) movement limitations	0	1	2	3	4	5	N/A
7. When walking up the stairs, do you have							
a) sensation of mesh	0	1	2	3	4	5	N/A
b) pain	0	1	2	3	4	5	N/A
c) movement limitations	0	1	2	3	4	5	N/A
8. While exercising, do you have							
a) sensation of mesh	0	1	2	3	4	5	N/A
b) pain	0	1	2	3	4	5	N/A
c) movement limitations	0	1	2	3	4	5	N/A

Date of Surgery: _____

FORM B: Patient Questionnaire

Date of Follow-up: _____

Since surgery, have you noticed any of the following at your surgical site:

1. Bulges or protrusions? (No) (Yes) _____
2. Drainage? (None) (Clear) (Bloody) (Yellow) (Other) _____
3. Pain (excluding expected surgical pain) ?
(None) (As expected) (Dull) (Stabbing) (Burning) (Numbness) Severity (0-10) _____
Since surgery; (Improving) (Constant) (Worsening) _____

Since discharge from the hospital, have you had any of the following symptoms:

4. Fever (>100.4)? (No) (Yes) Max Temp: _____
Bowel problems? (None) (Constipation) (Diarrhea) (Nausea) (Vomiting) _____

Since surgery, have you had any of the following:

5. Antibiotics by mouth? (No) (Yes) (Currently taking) (Completed)
Why was it prescribed? _____
Name of antibiotic: _____
When and how long did you take it? _____
6. Topical antibiotics for your surgical wound? (No) (Yes) Specify _____
(Bacitracin) (Neomycin) (Polymyxin) (Bactroban/mupirocin) (Silvadene)
7. An open wound requiring dressing changes? (No) (Yes)
What kind and frequency? _____
8. ER or hospital visits (related to surgery)? (No) (Yes) Specify _____

9. Since surgery, have you seen a doctor or surgeon at another institution about your wound, abdomen, or other issues related to your surgery? (yes) (no).
If yes, who? _____

FORM C: Abdominal Examination

Examiner: _____

Circle Appropriate Findings

Exam: Completely Normal

Incision: (clean/dry/intact) (necrosis) (breakdown) Describe other than normal findings:

If open wound: (since surgery) (reopened) length: _____ width: _____ depth: _____

Condition: (infected) (necrosis) (improving) (exudate) (granulation) (mesh exposed)

Dressing: (plain gauze) (iodoform) (wound vac) Describe: _____

Surrounding skin: (normal) (erythema) (cellulitis) (fluctuance) (induration)

Deep examination: (normal) (seroma) (granuloma) (abscess)

Drainage: (none) (serous) (serosang) (purulent) (other) _____

JP Drains:

1. (serous) (serosang) (purulent) last 24h output _____ (removed today)

2. (serous) (serosang) (purulent) last 24h output _____ (removed today)

3. (serous) (serosang) (purulent) last 24h output _____ (removed today)

Presence of Bulge: (none) (laxity) (hernia) size: _____ x _____ location: _____

Recurrent Hernia: (reducible) (incarcerated) Describe: _____

Assessment

Plan

FORM D: Data Collection

Demographics	PPI	Number of	Previous Wound	DVT
Age	Other	Operations	Complications	Diarrhea
Sex	No Medications	Estimated Blood	Surgical	Enterotomy
Race	Comorbidities	Loss	Technique	Fever
Financial Code	Alcoholism	Peritoneal	Previous Mesh	Hematoma
Case Type	Arrythmia	Malignancy	Ventral Location	Hernia Recurrence
Admission Date	Asthma	Time of Operation	# TA Sutures	Hypercarbia
Discharge Date	CHF	ASA Score	PostOperative	Hypertension
Length of Stay	Cirrhosis	Blood Transfusion	Analgesia	Hypoxia
OR Charges	COPD	Number of Units	Hydrocodone	Ileus
Total Charges	CAD	Estimated Blood	Dilaudid	Incisional Hernia
Weight	CVA	Loss	Demerol	Incision
Height	Diabetes	Platelet	Morphine	Numb/Ting
Body Mass Index	ESRD	Transfusion	Other	Infxn Unknown
Comments	HIV	Morphine	Analgesia Type	Origin
1° Diagnosis	Hypercholesterol	Equivalents (mg)	Mechanism	Intraabd Abscess
2° Diagnoses	Illicit Drugs	Intra-Operative	PCA/Pump	Kidney Infarction
1° Procedure	History of Cancer	Ultrasound	Epidural	Loss Pneumo
2° Procedures	Hyperlipidemia	Operation Time	IV	MI
Laboratory /	Hypertension	Pathology	Oral	Nausea
Radiology	Hyperthyroidism	Procedure	Other	Pancreatitis
CXR	Hypothyroidism	Identification	Complications	Enterotomy
Blood pressure	Morbid Obesity	Concomitant	Air Embolous	Pneumonia
Pulse	Pulmonary HTN	Procedure	Anast Leak	Pneumothorax
Glascow Coma	PVD	If Yes, type	Anast Stenosis	Postop
Urea	Sleep Apnea	Incarceration	Anesthesia	Hypotension
Sodium	Tobacco	If Yes, Organ	Complication	Prolong Incision
Potassium	Previous Intra-	Enterotomy Made	Atelectasis	Pain
Chloride	Abdominal	Mesh Used	Bladder Injury	Mesh Infection
Bicarb	Surgery	Current Mesh	Bleeding	Pulmonary
BUN	Abdominal	Defect Size	Bile Duct Injury	Embolism
Creatinine	Trauma	Mesh Size	Bowel Injury	Readmission 30
Glucose	Renal	Fibrin Glue	Cardiac	Days
Hemoglobin	Insufficiency	Postop Persistent	Arrhythmias	Renal Failure
WBC	Preop Anemia	Pain	Cardiac Failure	Reoperation
Platelet Count	Other	If Yes, Injected	Chest Pain	Resp Failure
ECG	No	# times per site	Colitis	Septicemia
Medications	Commorbidities	# sites injected	Constipation	Seroma
Steroids	Operative Record	Prev Abd Surgery	CVA	SBO
Coumadin	Operation Severity	Prev Hernia	Death	Splenic Injury
Anti-Platelet		Repair	Deep Infection	Subcutaneous
		If Yes, how many		Emphysema

Ureteral Injury	Wound
Urinary Retention	Dehiscence
Urine Leak	Wound Necrosis
UTI	Drain Placement
Vomiting	Drainage Clear
Other	Drainage (nos)
Follow-up Data	Drainage Purulent
Drains	EC Fistula
Wound Comp	Erythema
Non-related Comp	Inflammation
Visual Analog	Fistula
Scale	Hematoma
Date Return to	Wound Infection
Work	Local skin
Date Return	infection
Driving	Wound Abscess
Date Return	Deep Infection
Exercise	Mesh Infection
Preop Sym	Infected Seroma
Returned	Intraabd Infection
Oral Pain Med	Intraabd Abscess
Amt	Ischemia
Patient Feels Mesh	Seroma
Patient has Pain	Seroma
Pain Location	Intervention
Pain Exercise Only	Wound
Date No Postop	Intervention
Pain	Wound Vac
Hernia Sites	
Injected	
